## List of Abbreviations

AE	Adverse Event
AVPU	Alert, Voice, Pain, Unresponsive
CABG	Coronary Artery Bypass Surgery
CKMB	Creatinine Kinase-MB
CRF	Case Report Form
eCRF	Electronic Case Report Form
ED	Emergency Department
FDA	Food and Drug Administration
GCP	Good Clinical Practice
GCS	Glasgow Coma Score
HIPAA	Health Insurance Portability and Accountability Act
HRV	Heart Rate Variability
IABP	Intra-aortic Balloon Pump
IB	Investigator's Brochure
ICU	Intensive Care Unit
IRB	Institutional Review Board
MEWS	Modified Early Warning Score
MI	Myocardial infarction
NEWS	National Early Warning Score
PCI	Percutaneous Coronary Intervention
PHI	Protected Health Information
PI	Principal Investigator
SAE	Serious Adverse Event
SpO2	Oxygen Saturation
SOP	Standard Operating Procedure
VT	Ventricular Tachycardia

## Protocol Summary

Title	Verification of a Prediction Algorithm for Cardiopulmonary Patients Admitted to the Emergency Department
Short Title	Verification of Prediction Algorithm
Study Design	Prospective observational clinical study
Study Duration	Estimated duration: 18 Months
Study Site(s)	3 Sites
Objective(s)	Verify existing prediction algorithm of cardiopulmonary events. Assess the prediction algorithm with regard to the frequency of cardiopulmonary events
Primary Analysis	Regression analysis
Number of Subjects	760 subjects
Subject Eligibility Criteria	
Inclusion Criteria
 
Candidates for this study must meet all of the following Inclusion criteria:
 

1. 18 years of age or older

2. Admission to emergency department requiring immediate medical attention due to presumed cardiac or pulmonary cause(s) and considered 2nd or 3rd tier priority in triage system.

 
Exclusion Criteria
 
Candidates will be excluded from the study if any of the following conditions are present:
 

1. Pregnant or suspected pregnancy

2. Significant trauma

3. Do Not Resuscitate order

4. Known as ward of the state

## 1 *Introduction*

### 1.1 *Background*

The best method by which to triage patients presenting to the emergency department (ED) has yet to be established. The key objective of the process of triage is to determine which patient is at the highest risk because that patient will require the greatest amount of resources and attention to determine the most appropriate treatment. Risk stratification is a necessary method for triaging patients, particularly in the ED, as the number of patients presenting to the ED and the availability of staff is never equally matched requiring a method to determine the order and urgency in which patients are treated.

Recent scoring systems to determine risk of significant clinical deterioration in patient health, such as the Modified Early Warning Score (MEWS), utilize vital signs (i.e., heart rate, respiration rate, blood pressure, temperature, pulse oximetry) and a subjective measure of the patient's mental status (i.e., AVPU score: alert, reacts to voice, reacts to pain, or unconscious). Elevated MEWS values has been shown to be related to mortality. In the United Kingdom, a national early warning score (NEWS) has been implemented nationwide and been shown to discriminate patients at risk of the combined outcome of cardiac arrest, unanticipated intensive care unit (ICU) admission, or death within 24 hours.

A novel algorithm for determining risk of acute cardiac complications, including cardiac arrest, for patients presenting to the ED has recently been reported. Unlike prior risk stratification tools that relied on basic vital sign data, this algorithm utilizes multiple metrics of heart rate variability (HRV) as well as a machine learning approach to solve the risk classification problem. The algorithm requires the collection of vital sign data, patient mental status, and *at least* 5 minutes of continuous electrocardiography (to calculate HRV metrics). It was shown to be more accurate than MEWS in predicting cardiac arrest within 72 hours of admission to hospital. Furthermore, the algorithm has been used to predict serious complications (mortality, cardiac arrest, ventricular tachycardia, hypotension requiring inotropes or intra-aortic balloon pump (IABP) insertion, intubation or mechanical ventilation, complete heart block, bradycardia requiring pacing, and recurrent ischemia requiring revascularization) within 72 hours in patients presenting to the ED with chest pain. In this patient population, a score of 4 or higher from the algorithm had a sensitivity of 0.880, specificity of 0.680, positive predictive value of 0.195, and a negative predictive value of 0.985 which was better than using ST elevation/depression and troponin in predicting complications within 72 hours. The primary limitation of the algorithm is that it has been developed and tested in Singaporean patients. Verification of the results of the studies using this algorithm in other patient cohorts is required. As such, the proposed study will investigate the sensitivity and specificity of the algorithm.

## **1.2 *Risks/Benefits***

### **1.2.1 *Risks***

This is an observational study. The only risk is a breach of the patient's protected health information.

If a patient or LAR is unwilling or unable to sign Informed Consent the data will be removed from the database and not be considered in the final analysis. These patients not participating will be replaced to ensure that the number of patients approved for this study is met.

### **1.2.2 *Benefits***

There is no benefit to an individual enrolled in this study. The benefit of this study is the verification of the algorithm.

## **2 *Study Protocol***

### **2.1 *Study Design***

#### **2.1.1 *Purpose***

The purpose of this study is to verify an existing algorithm used to predict cardiopulmonary events in patients presenting to the emergency department.

#### **2.1.2 *Scope and Duration***

This is a prospective, multi-center, observational study.

Enrollment in this study is expected to take approximately 18 months. Subjects are enrolled upon arrival to the emergency department and followed for 72 hours.

#### **2.1.3 *Sample Size***

Approximately 760 subjects will be enrolled in this study.

#### **2.1.4 *Study Objectives***

##### **2.1.4.1 *Primary Objective***

The primary objective is to verify an existing prediction algorithm of cardiopulmonary events.

### **2.1.4.2 Secondary Objective**

The secondary objective is to assess the prediction algorithm with regard to the frequency of cardiopulmonary events.

### **2.1.5 Primary Outcome Measure**

#### **2.1.5.1 Cardiopulmonary events**

Cardiopulmonary events will be measured as the occurrence of any cardiopulmonary event, not limited to:

Cardiac arrest

Sustained ventricular tachycardia (VT)

Hypotension requiring inotropes or intra-aortic balloon pump (IABP) insertion

Intubation or mechanical ventilation

Complete heart block

Bradycardia requiring insertion of a pacing wire or external pacing, and

Percutaneous coronary intervention (PCI) or coronary artery bypass surgery (CABG),

\*all within 72 hours of presentation to the ED

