## 2.2.2 Inclusion Criteria

Candidates for this study must meet all of the following Inclusion criteria:

1. 18 years of age or older;
2. Admission to emergency department requiring immediate medical attention which is presumed to be cardiac or cardiopulmonary related and considered 2nd or 3rd tier priority in triage system. Symptoms including:
  - Shortness of breath
  - Skin pallor consistent with cardiopulmonary complications
  - Chest pain
  - Rapid or irregular heartbeat

And any symptoms considered to be cardiac or cardiopulmonary-related by the investigator

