## 2.3 Study Procedures

Schedule of Events			
Hospital Stay Status	Admit	During	Discharge/ Withdrawal
Inclusion/Exclusion Criteria	X		
Informed Consent	X 		
Study Evaluations			
Demographics (date of birth/age, gender and ethnicity)	X		
Smoking status	X		
ED diagnosis (primary)	X		
Final diagnosis (primary)			X
Medications including beta-blockers, combined alpha and beta-blockers, digitalis, calcium channel blocker, bronchodilators, amiodarone, other anti-arrhythmics	X	X	X

Medical history, specifically a history of ischemic heart disease, diabetes, hypertension, dyslipidemia, stroke, cancer, respiratory disease, renal disease, congestive heart disease, PCI, CABG, MI)	X		
Physical exam [REDACTED]	X		
Glasgow Coma Score (GCS)	X		
Blood labs; specifically troponin and/or CKMB if available	X		
12-lead ECG (if patient is reporting chest pain)	X 		
Continuous 3-lead ECG recording of at least five minutes	X		
Chest Pain	X		
Symptom onset/peak within 24 hours of presentation	X		
Pain score	X		
MEWS Score	X		
Cardiopulmonary events (acute pulmonary edema, lethal arrhythmias, cardiogenic shock, myocardial infarction, percutaneous coronary intervention, coronary artery bypass surgery, recurrent ischemia requiring revascularization)	X	X	X
In-hospital cardiac arrest		X	
In-hospital death		X	
Status changes (admitted to ICU, admitted to ward, etc.)		X	
Length of stay			X
Adverse Events	X	X	X

1 Every effort will be made to ensure that consent is received from the patient or patient's legally authorized representative (LAR) within 24 hours of patient enrollment. If the patient or LAR refuses consent the patient will be withdrawn from the study.

[figure not shown]
2 If applicable

3 Serious adverse events must be reported to the Sponsor within 24 hours of becoming aware of the event, but no later than 10 days after the event.

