### 2.3.2 Evaluation Requirements

#### 2.3.2.1 Assessments

The following data points will be recorded:

- Inclusion/Exclusion Criteria
- Demographics (date of birth/age, gender and ethnicity)
- Smoking status
- ED diagnosis (primary)
- Final diagnosis (primary)
- Medications including beta-blockers, combined alpha and beta-blockers, digitalis, calcium channel blocker, bronchodilators, amiodarone, other anti-arrhythmics

- Medical history, specifically a history of ischemic heart disease, diabetes, hypertension, dyslipidemia, stroke, cancer, respiratory disease, renal disease, congestive heart disease, PCI, CABG, MI)
- Physical exam [REDACTED]  
[REDACTED]  
[REDACTED]
- 12-lead ECG (if patient is reporting chest pain)
- Continuous 3-lead ECG recording of *at least* five minutes within 30 minutes of ED triage
- Chest Pain
- Symptom onset/peak within 24 hours of presentation
- Pain score
- MEWS Score
- Cardiopulmonary events (acute pulmonary edema, lethal arrhythmias, cardiogenic shock, myocardial infarction, percutaneous coronary intervention, coronary artery bypass surgery, recurrent ischemia requiring revascularization)
- In-hospital cardiac arrest
- In-hospital death
- Status changes (admitted to ICU, admitted to ward, etc.)
- Length of stay

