## **3.2 Primary Outcome Measure**

The primary outcome measure is the occurrence of cardiopulmonary events. It will be measured as the occurrence of any cardiopulmonary event, within 72 hours of presentation to the ED, including:

Cardiac arrest

Sustained ventricular tachycardia (VT)

Hypotension requiring inotropes or intraaortic balloon pump (IABP) insertion

Intubation or mechanical ventilation

Complete heart block

Bradycardia requiring insertion of a pacing wire or external pacing, and

Percutaneous coronary intervention (PCI) or coronary artery bypass surgery (CABG).

For the primary outcome measure of occurrence of cardiopulmonary events, binary logistic regression will be used to estimate the probability that a cardiopulmonary

event has occurred given the values of explanatory variables, given by the following equation:

- $Y$  is the primary outcome measure  
 $Y_i = 1$  if a cardiopulmonary event has occurred  
 $Y_i = 0$  if there is no cardiopulmonary event
- $\pi_i$  = the probability of a cardiopulmonary event
- $X = (X_1, X_2, \dots, X_k)$  being the set of explanatory variables

*Model:*

$$\text{logit}(\pi_i) = \beta_0 + \beta_1 x_{i1} + \dots + \beta_k x_{ik}$$

A Receiver Operating Characteristic Curve will be constructed and the area under the curve will be calculated to assess the model sensitivity.

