### **3.5 Blinding**

This study is observational and no blinding will occur.

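### The primary outcome is an open list, and the schedule gives the same label to a different set of events, so a presenting MI or pulmonary edema can be scored as an event or not depending on the section followed

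*Combined protocol and SAP*

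**What the plan says.** Section 2.1.5.1 defines the primary outcome: "Cardiopulmonary events will be measured as the occurrence of any cardiopulmonary event, not limited to". Seven items follow: cardiac arrest; sustained VT; hypotension needing inotropes or a balloon pump; intubation or ventilation; complete heart block; bradycardia needing pacing; and PCI or CABG. The window is "all within 72 hours of presentation to the ED".

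Section 3.2, which defines Y for the logistic model, gives the same seven items with a different lead-in: "It will be measured as the occurrence of any cardiopulmonary event, within 72 hours of presentation to the ED, including".

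The schedule in 2.3, repeated as a data list in 2.3.2.1, describes what is recorded: "Cardiopulmonary events (acute pulmonary edema, lethal arrhythmias, cardiogenic shock, myocardial infarction, percutaneous coronary intervention, coronary artery bypass surgery, recurrent ischemia requiring revascularization". In the schedule this row is marked at Admit, During and Discharge/Withdrawal. In-hospital cardiac arrest and in-hospital death have their own rows. Section 2.1.6.1, on the frequency of cardiopulmonary events, also counts MI and acute pulmonary edema.

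Entry under 2.2.2 requires an ED admission "requiring immediate medical attention which is presumed to be cardiac or cardiopulmonary related and considered 2nd or 3rd tier priority in triage system". The symptom list ends "And any symptoms considered to be cardiac or cardiopulmonary-related by the investigator".

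Of all these events, only cardiac arrest is given a definition (2.1.6.2). No section closes the list, says who decides what else counts, requires an event to be new, or excludes the presenting diagnosis.

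**The concern.** The study exists to verify an algorithm, and Section 1.1 says its sensitivity and specificity will be investigated. Those quantities have meaning only against a fixed outcome. Here the set of qualifying events is not fixed, and under the protocol's own labels it overlaps with conditions that can bring a patient into the study.

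A patient with chest pain may prove to have an MI, and one with shortness of breath may have acute pulmonary edema. The protocol elsewhere calls both conditions cardiopulmonary events, and neither is among the seven items. Whether such a patient is an event or a non-event changes the numerator and denominator of every accuracy measure, as well as the response variable in the regression.

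**Working it through.** **1. The sections side by side.** Take a patient who presents with MI, has no PCI or CABG within 72 hours, and has none of the other five listed items.

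- 2.1.5.1 read literally: the list is not exhaustive and the schedule names MI as a cardiopulmonary event, so Y=1.
- 3.2 read as a seven-item composite: Y=0.
- 3.2 read literally: its lead-in also covers any cardiopulmonary event, so Y=1.

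The same holds for presenting pulmonary edema. Death is undecided too. The composite of the chest-pain study described in 1.1 includes mortality, but the seven items do not. A death that does not meet the arrest definition in 2.1.6.2 counts only if the open wording is used.

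In the other direction, the schedule rows do not name intubation or ventilation, complete heart block, pacing, or hypotension needing inotropes or a balloon pump: four of the seven items.

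**2. The plan's own figure.** Section 3.7 gives 634 analysed. Hsieh's 1989 formula is n = [z(0.975) + z(0.80)·exp(−β²/4)]²·(1 + 2Pδ)/(Pβ²), with δ = [1 + (1+β²)·exp(5β²/4)]/[1 + exp(−β²/4)]. With β = 0.747 and P = 0.050 it gives 317.1. Dividing by (1 − 0.5) gives 634.2, which matches 634 when 0.500 is taken as the squared multiple correlation. The calculation assumes 5% events at the mean of x, about 6.2% overall for a standard normal x. Nothing ties that rate to a closed or an open list.

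**3. Illustration of size.** Inputs from the documents: 634 analysed (3.7); sensitivity 0.880, specificity 0.680 and PPV 0.195 at a score of 4 or higher (1.1). Two listed-event rates are used:

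- 5%, borrowed from 3.7;
- 8%, implied by 1.1: 0.195×0.32/(0.88×0.805 + 0.195×0.32) = 0.0624/0.7708 = 0.081.

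Assumed, with no source in the documents: unlisted events are counted in 5% or 10% of subjects without a listed event.

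Let E be listed events, U unlisted events, and f the share of unlisted events scoring 4 or higher. Apparent sensitivity = (0.88E + fU)/(E + U). If unlisted events are unrelated to the score, f = 1 − 0.680 = 0.32.

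| Listed rate | E | Extra | U | Event rate | Apparent sensitivity |
|---|---|---|---|---|---|
| 5% | 31.7 | 5% | 30.1 | 9.8% | (27.9 + 9.6)/61.8 = 0.61 |
| 5% | 31.7 | 10% | 60.2 | 14.5% | (27.9 + 19.3)/91.9 = 0.51 |
| 8% | 50.7 | 5% | 29.2 | 12.6% | (44.6 + 9.3)/79.9 = 0.68 |
| 8% | 50.7 | 10% | 58.3 | 17.2% | (44.6 + 18.7)/109.0 = 0.58 |

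**4. Direction.** The formula shows that apparent sensitivity falls if f is below 0.88 and rises if it is above. Apparent specificity rises if f exceeds 0.32. At the 5% listed rate with 5% extra events, f = 0 gives 27.9/61.8 = 0.45 and f = 1 gives (27.9 + 30.1)/61.8 = 0.94. The documents give no value for f. The algorithm uses heart rate variability and vital signs (1.1), which a presenting arrhythmia or pulmonary edema may alter, so f need not be near 0.32.

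**The case against.** The strongest reply is that the sponsor intends a closed seven-item composite. Section 3.2 is the section that defines Y, it omits the phrase that makes 2.1.5.1 explicitly open, and its items are major complications or interventions, in line with the serious complications described in 1.1. The data list also names specific events and has no catch-all item. This is a plausible reading of intent. It does not close the list, because the lead-in in 3.2 still reaches any cardiopulmonary event. Nor does it explain why the schedule uses that label for another set.

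Four stronger readings are tempting but unsupported:

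- *A typical enrollee becomes an event.* The named entry symptoms are not themselves listed events. Conditions such as a COPD exacerbation or rapid atrial fibrillation are not named as events anywhere. The documented overlap concerns conditions the protocol itself labels as events, MI and acute pulmonary edema in particular.
- *Sites will score differently.* Three sites, open wording, no described adjudication and the statement "This study is observational and no blinding will occur" make this possible. The documents do not say it will happen, and the CRF completion instructions mentioned in 5.2.3 are not available to check.
- *Sensitivity will be understated.* That requires extra events largely unrelated to the score. The opposite is possible.
- *The list will be extended after data are seen.* Nothing prevents it, but nothing plans it.

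It is also fair to say that 0.880 and 0.680 come from chest-pain patients with a somewhat different composite, and that 3.2 specifies logistic regression and AUC without a cutoff.

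**Conclusion.** The point holds as a defect of definition. Y is not fixed: 2.1.5.1, 3.2 and the schedule support at least two scorings of the same patient, and following the stated rule literally makes some presenting diagnoses events. Confidence is high on the wording.

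The size is illustrative. With unlisted events unrelated to the score in 5% or 10% of the other subjects, sensitivity of 0.88 would appear as about 0.61 or 0.51 at a 5% listed-event rate, or 0.68 or 0.58 at 8%. Those extra-event rates are assumptions. If the extra events are related to the score, performance could be inflated instead, so no direction of bias should be claimed. The uncertainty about direction does not rescue the definition, because the result would still depend on the reading chosen.

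**What to change.** 1. Use one closed list, worded identically in 2.1.5.1 and 3.2: any one of the following, and no other event.
2. State explicitly whether a death that does not meet the arrest definition in 2.1.6.2 is in the list. Closing the list at the present seven items without this decision would silently leave such deaths out.
3. State that a presenting diagnosis does not count unless it meets a listed item.
4. Align the event items in 2.3, 2.3.2.1 and the eCRF to that list, so that every component of Y has a named field.
5. Record other cardiopulmonary events descriptively, outside Y.

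The cost is a wording change in the outcome sections and the alignment of a few schedule and eCRF items. The downside is that clinically relevant unlisted events are reported only descriptively.

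### The primary composite differs from the published composite the study sets out to verify, and no planned analysis uses the published one or reports sensitivity and specificity at its cut-off

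*Combined protocol and SAP*

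**What the plan says.** Section 1.1 gives the benchmark. The published 72-hour composite is described as "serious complications (mortality, cardiac arrest, ventricular tachycardia, hypotension requiring inotropes or intra-aortic balloon pump (IABP) insertion", then intubation or ventilation, then "complete heart block, bradycardia requiring pacing, and recurrent ischemia requiring revascularization) within 72 hours in patients presenting to the ED with chest pain". In that cohort a score of 4 or higher "had a sensitivity of 0.880, specificity of 0.680, positive predictive value of 0.195, and a negative predictive value of 0.985". The section names testing only in Singaporean patients as the main limitation, says that "Verification of the results of the studies using this algorithm in other patient cohorts is required", and concludes that "the proposed study will investigate the sensitivity and specificity of the algorithm".

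The primary outcome (section 2.1.5.1, repeated in section 3.2) carries over the other non-fatal components. It does not list death, it qualifies VT as sustained, and its last component is "Percutaneous coronary intervention (PCI) or coronary artery bypass surgery (CABG". Elsewhere the plan treats these procedures as distinct from "recurrent ischemia requiring revascularization": the Schedule of Events (section 2.3) and the secondary outcome (sections 2.1.6.1 and 3.3) list PCI, CABG and that item separately.

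The planned analyses are a logistic regression with ROC curve and AUC on the primary composite (section 3.2), a linear regression on the number of events from a different list (section 3.3), and two missing-data scenarios (section 3.6).

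**The concern.** A study whose purpose is to verify a published result needs at least one analysis on the endpoint behind that result. Here a reader who sets the findings beside 0.880 and 0.680 compares different patients and different endpoints at once. The difference in patients is the object of the study. The difference in endpoint can be avoided. A lower sensitivity could come partly from the definition, and a matching one could come from offsetting differences. Section 3 also never produces sensitivity and specificity at the published cut-off, so the comparison promised in section 1.1 has no planned analysis behind it.

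**Working it through.** **1. The two composites side by side**

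| Component | Published, as described in 1.1 | Primary, 2.1.5.1 and 3.2 |
|---|---|---|
| Death | Listed | Not listed; 2.1.6.2 counts sudden unexpected death as cardiac arrest |
| VT | Unqualified | Sustained only |
| Revascularization | For recurrent ischemia | PCI or CABG, no qualifier |
| Cardiac arrest; hypotension with inotropes or IABP; intubation or ventilation; complete heart block; bradycardia with pacing | Listed | Listed |

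Section 2.1.5.1 also leaves its list open-ended.

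**2. Does any planned analysis restore the published composite?** No. Section 3.2 uses the primary composite. The section 3.3 list includes death and recurrent ischemia, but does not name intubation, heart block, pacing, or hypotension requiring inotropes or IABP, and it is analysed as a count. Section 3.6 varies only the handling of missing data.

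**3. Event rate implied by the benchmark.** Inputs from section 1.1: sensitivity 0.880, specificity 0.680, PPV 0.195.

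- Odds of an event = PPV/(1 − PPV) × (1 − specificity)/sensitivity = (0.195/0.805) × (0.320/0.880) = 0.0881
- Event rate p = 0.0881/1.0881 = 0.081
- Check: NPV = 0.680 × 0.919/(0.680 × 0.919 + 0.120 × 0.081) = 0.985, which reproduces the stated NPV.

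**4. Effect of the revascularization change alone, with patients and scores held fixed.** Two quantities are assumptions, not in the documents: q, the further proportion of patients with PCI or CABG not for recurrent ischemia, and r, the share of them scoring 4 or higher. The range for r runs from 0.32 (they score like non-events, 1 − 0.680) to 0.88 (they score like events).

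- New sensitivity = (0.880p + qr)/(p + q)
- New specificity = (0.680(1 − p) − q(1 − r))/(1 − p − q)

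| q | r | Sensitivity | Specificity |
|---|---|---|---|
| 2% | 0.32 | 0.769 | 0.680 |
| 2% | 0.60 | 0.825 | 0.686 |
| 2% | 0.88 | 0.880 | 0.692 |
| 5% | 0.32 | 0.666 | 0.680 |
| 5% | 0.60 | 0.773 | 0.696 |
| 5% | 0.88 | 0.880 | 0.712 |

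Example, q = 5% and r = 0.32: (0.880 × 0.081 + 0.05 × 0.32)/(0.081 + 0.05) = 0.0872/0.131 = 0.666.

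The effects of dropping mortality and of restricting VT are not in this table; the documents give nothing from which to size them.

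**5. Scale against sampling error.** With 634 analysed (section 3.7), an 8.1% rate gives about 51 events. The 95% half-width for a sensitivity of 0.88 is then 1.96 × √(0.88 × 0.12/51.4) = 0.089. At a 5% rate (about 32 events) it is 0.113. The possible definition effect therefore runs from nothing to more than the sampling error.

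**6. Are the data there?** The Schedule and section 2.3.2.1 name in-hospital death, recurrent ischemia requiring revascularization, and chest pain. They do not name intubation, heart block, pacing, or hypotension with inotropes or IABP. The sponsor's own primary composite needs those items, so they must be captured somewhere, but the documents do not show it.

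**The case against.** The strongest case against runs as follows.

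- **The endpoint is not the only confounder.** A reader might infer that the changed endpoint is what prevents a difference from being attributed to the new population, or that matching the composite would isolate the population. The documents support neither. The benchmark came from patients with chest pain. Section 2.2.2 also admits shortness of breath, pallor, rapid or irregular heartbeat, and any symptom the investigator judges cardiac or cardiopulmonary. Case mix would differ even with an identical composite. This stands, and it is why the point is limited to one avoidable confounder among others.
- **A large drop is not established.** A reader might infer a definite fall in sensitivity. The fall depends on r, for which there is no source; at r = 0.88 there is none. This stands.
- **The published definition is known only from one sentence.** PCI or CABG could be the sponsor's operational wording for the revascularization item. That is possible, but the plan lists the terms separately elsewhere, which points the other way. That the broader component would take in routine early procedures is an inference; no section says so.
- **Mortality is partly covered.** Sudden unexpected death counts as cardiac arrest, in-hospital death is in the secondary list, and the open-ended primary list might admit death. None of this amounts to all deaths within 72 hours counting in the primary composite.
- **An exact match may be out of reach.** In-hospital death is not quite 72-hour mortality, since the Schedule shows no contact after discharge. VT may not be recoverable without the sustained qualifier. This stands; the added analysis would be closer to the benchmark, not identical to it.
- **The figures 0.880 and 0.680 are background, not a success criterion, and section 1.1 cites more than one study.** That is correct, but section 1.1 still commits the study to sensitivity and specificity, and section 3 provides neither at a cut-off.

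**Conclusion.** The point holds as a should-fix improvement, not as a fault that invalidates the primary analysis. The composites differ in three respects (death, VT, revascularization), and no planned analysis uses the published composite or reports accuracy at score 4 or higher. The definition is thus an avoidable confounder alongside case mix.

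Its size is unknown. With an event rate of 8.1% and an assumed further 2% to 5% of patients with other PCI or CABG, sensitivity lies between 0.880 and about 0.77 (2%) or 0.67 (5%), and specificity between 0.680 and about 0.69 or 0.71. These ranges rest on the assumed q, on r lying between 0.32 and 0.88, and on the benchmark cohort's event rate applying here. They cover the revascularization change only.

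Nothing here shows that the sponsor's broader composite is the wrong choice of primary.

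**What to change.** Keep the primary composite and the planned 634. Add a pre-specified supplementary analysis to section 3:

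- **Endpoint:** the composite described in section 1.1, within 72 hours of presentation. Add death, count revascularization only when recorded as for recurrent ischemia (with a stated rule for separating it from other PCI or CABG), and match the VT definition as closely as the data allow.
- **Measures:** sensitivity and specificity at score 4 or higher, with 95% CIs, shown beside 0.880 and 0.680.
- **Populations:** all analysed subjects, and those with chest pain. Name the chest-pain result as the closest like-for-like comparison, and list the remaining differences.
- **Data check:** confirm that the eCRF records each component separately, in particular those not named in the Schedule or section 2.3.2.1.

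The cost is a short addition to the SAP, the eCRF check, and one more reported analysis. That analysis will have fewer events and wider intervals than the primary, particularly in the chest-pain subset, so it should be presented as estimation and not as a pass-or-fail test.
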